8.3. Adverse Events, Serious Adverse Events and other safety reporting

8.3.1. Time period and frequency for collecting AE, SAE and other safety information

Table 11 Timeframes for collecting and reporting of safety information

Event	Screening*	Visit 1		Visit 2		Visit 3		Visit 4	Visit 5	Phone call
	Up to 56 days before Visit 1	Day 1	Day 7	Day 8	Day 28	Day 29	Day 35	Day 36	Day 57	Day 209
Event	Up to 56 days before Visit 1	Dose 1	7 days post-Dose 1		28 days post-Dose 1	Dose 2	7 days post-Dose 2		28 days post-Dose 2	Study conclusion
Administration site and systemic solicited events										
Unsolicited AEs										
MAEs pIMDs										
SAEs (all, fatal, related) AEs/SAEs leading to withdrawal from the study										
SAEs related to study participation or concurrent GSK medication/vaccine										
Pregnancies and outcome										

AE: adverse event; MAE: medically attended event; pIMD: potential immune-mediated disease; SAE: serious adverse event

*i.e., consent obtained

The investigator or designee will record and immediately report all SAEs in enrolled participants to the sponsor or designee via the Expedited AE Reporting Form. Reporting should, under no circumstances, occur later than 24 hours after the investigator becomes aware of an SAE, as indicated in Section 10.3.11. The investigator will submit any updated SAE data to the sponsor within 24 hours of it being available.

A post-study AE/SAE is defined as any event that occurs outside of the AE/SAE reporting periods defined in [Table 11](#). Investigators are not obligated to actively seek AEs or SAEs from former study participants. However, if the investigator learns of any SAE, including a death, at any time after a participant has been discharged from the study, and if the investigator considers the event to be reasonably related to the study intervention, the investigator will promptly notify the study contact for reporting SAEs mentioned in the [Table 13](#).

8.3.2. Method of detecting AEs and SAEs, pregnancies and other events

Detection and recording of AE/SAE/pIMD/pregnancies are detailed in Section [10.3.9](#).

Assessment of AE/SAE intensity, causality and outcome are described in Section [10.3.10](#).

Open-ended and non-leading verbal questioning of participants is the preferred method of acquiring information related to an AE/SAE/pIMD/pregnancy.

8.3.2.1. Clinically significant abnormal laboratory findings

The investigator must review the laboratory report, document that the review occurred, and record any clinically relevant changes occurring during the study in the AE section of the eCRF. Clinically significant abnormal laboratory findings are those which are not associated with an underlying disease, unless judged by the investigator to be more severe than expected for the participant's condition.

- All clinically significant abnormal laboratory test values reported during the study or within 28 days after the last dose of study intervention should be repeated until the values return to normal/baseline, or until they are no longer considered significantly abnormal by the investigator. Refer to Section [10.3.7](#) for more information on clinically abnormal laboratory assessments that qualify as an AE or SAE.
- If such values do not return to normal/baseline after an interval judged reasonable by the investigator, the etiology of the abnormal value should be identified, and the sponsor notified.

8.3.3. Regulatory reporting requirements for SAEs, pregnancies and other events

Once an investigator (or designee) becomes aware that a study participant has experienced an SAE/pIMD/pregnancy, it must be reported to GSK using the required

documentation and within the timeframes mentioned in [Table 12](#). This is essential for GSK to meet legal obligations and ethical responsibilities for participant safety and the safety of a study intervention under clinical investigation.

For SAEs/pIMDs, the investigator must always provide an assessment of causality at the time of the initial report, as defined in the Section [10.3.10.2](#).

Local regulatory requirements and sponsor policy for preparation of an investigator safety report of SUSAR must be followed. These reports will be forwarded to investigators as necessary.

The sponsor has the legal responsibility to notify local authorities/regulatory agencies about the safety of an investigational study intervention. The sponsor will comply with country-specific regulatory requirements related to safety reporting to the regulatory authority, IRB/IEC and investigators.

Please refer to Section [10.3.11](#) for further details regarding the reporting of SAEs/pIMDs/pregnancies.

Table 12 Timeframes for submitting SAE, pregnancy and other events reports to GSK

Type of event	Initial reports		Follow-up of relevant information on a previous report	
	Timeframe	Documents	Timeframe	Documents
SAEs	24 hours* [#]	electronic Expedited Adverse Events Report	24 hours*	electronic Expedited Adverse Events Report
Pregnancies	24 hours*	electronic pregnancy report	24 hours*	electronic pregnancy report
pIMDs	24 hours** ##	electronic Expedited Adverse Events Report	24 hours*	electronic Expedited Adverse Events Report

* Timeframe allowed after receipt or awareness of the information by the investigator/site staff.

**Timeframe allowed once the investigator determines that the event meets the protocol definition of a pIMD.

#For each SAE/pIMD, the investigator(s) must document in the medical notes that they have reviewed the SAE/pIMD and have provided an assessment of causality.

8.3.4. Treatment of expedited adverse events (SAE/pIMD)

Any medication administered for the treatment of an SAE/pIMD should be recorded in the Expedited Adverse Event Report of the participant's eCRF screen (refer to Section 10.3.11.1).

8.3.5. Participant card

The investigator (or designee) must provide the participant with a “participant card” containing information about the clinical study. The participant must be instructed to always keep the participant card in their possession for the duration of the study. In an emergency, this card serves to inform the responsible attending physician/family member that the participant is in a clinical study and that relevant information may be obtained by contacting the investigator(s) or their back-up.

8.3.6. Safety follow-up call

At 6 months post-Dose 2 telephone contacts, participants will be queried in accordance with a template script provided separately by GSK. Participants will be queried about concomitant medications, any intercurrent medical conditions, and the occurrence of pIMDs, SAEs, concurrent vaccination, SAEs related to study participation or to a concurrent GSK medication/vaccine, and AEs or SAEs leading to withdrawal.

Information collected will be documented in the source document and will be recorded in the eCRF.

8.4. Pharmacokinetics

Not applicable.

8.5. Genetics

In this study, genetics may be evaluated after review by the ethical review committee in accordance with the Japanese Ethical Guidelines for Medical and Biological Research Involving Human Subjects.

A 30 mL blood sample (PBMC) for DNA isolation will be collected at Visits 1, 3 and 5 (Days 1, 29 and 57) from participants who have consented to participate in the genetic research of the study.

Participants who do not wish to participate in the genetic research may still participate in the study.

See Section [10.5](#) for information regarding genetic research.

8.6. Biomarkers

Not applicable.

8.7. Immunogenicity assessments

Immunogenicity is described in Section [8.1](#).

8.8. Health outcomes

Not applicable.

9. STATISTICAL CONSIDERATIONS

9.1. Statistical hypotheses

No formal statistical hypotheses are to be tested. All analyses will be descriptive.

9.2. Analysis sets

Table 14 Analysis sets

Analysis set	Description
Screened set	All participants who were screened for eligibility
Enrolled set	All participants who entered the study (who were randomized or received study intervention or underwent a post-screening procedure)
Exposed Set (ES)	All participants who will receive at least 1 dose of the study intervention.
Per Protocol for immunogenicity set (PPS_Immuno)	All eligible participants who will receive all doses as per protocol, will have immunogenicity results post-dose, will comply with dosing/blood draw intervals, without intercurrent conditions that may interfere with immunogenicity and without prohibited concomitant medication/vaccination. The analysis will be done according to the study intervention that participants received at dose 1.
Per Protocol for CMI set (PPS_CMI)	All eligible participants who will receive all doses as per protocol, will have CMI results post-dose, will comply with dosing/blood draw intervals, without intercurrent conditions that may interfere with immunogenicity and without prohibited concomitant medication/vaccination. The analysis will be done according to the study intervention that participants received at dose 1.

CCI

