Recording of MAEs (Section 8.3)		●	●	●	●	●	●
Recording of SAEs (Section 8.3)		●	●	●	●	●	●
Recording of SAEs related to study participation or to a concurrent GSK medication/vaccine (Section 8.3)	●	●	●	●	●	●	●
Recording of pIMDs (Section 8.3)		●	●	●	●	●	●
Recording of AEs leading to withdrawal from the study intervention or withdrawal from study (Section 7)		●	●	●	●	●	●
Recording of pregnancies and pregnancy outcome (Section 8.3)		●	●	●	●	●	●
Study conclusion (Section 4.4)							●

AE: adverse event; CMI: cell-mediated immunity; CCI: cell-mediated immunity; MAE: medically attended event; PBMC: peripheral blood mononuclear cell; pIMD: potential immune-mediated disease; SAE: serious adverse event.

Note: The double-line borders indicate the analyses which will be performed on all data obtained up to these timepoints (refer to Section 9.3.5).

● is used to indicate a study procedure that requires documentation in the individual electronic Case Report Form (eCRF).

○ is used to indicate a study procedure that does not require documentation in the individual eCRF.

* Screening evaluations may be completed up to 56 days before Visit 1 (Day 1). Study staff should allow sufficient time between the Screening visit and Visit 1 to receive and review HSV testing results, and hematology/biochemical results. If deemed necessary by the investigator, re-testing can be performed within the allowed interval. Only data from the re-sampling testing, if done, will be taken into consideration.

** Blood sampling and pregnancy test to be performed before each study intervention administration.

CONFIDENTIAL218459 (TH HSV REC-004)
Protocol Final

*** The preferred location for measuring temperature will be the oral cavity. Study intervention administration should not occur in case of fever (defined as temperature $\geq 38.0^{\circ}\text{C}$, regardless of the location of measurement).

Optional blood sampling. A separate informed consent form (ICF) will be signed by participants who agree to give their blood sample for this optional blood sampling.

Table 2 **Intervals Between Study Visits**

Interval	Reference Visits	Planned Visit Interval	Allowed Interval Range
Screening (Day -56) → Visit 1 (Day 1)	Screening visit		Up to 56 days*
Visit 1 (Day 1) → Visit 2 (Day 8)	Study intervention administration Dose 1	7 days	7 – 9 days
Visit 1 (Day 1) → Visit 3 (Day 29)		28 days	28 – 33 days**
Visit 3 (Day 29) → Visit 4 (Day 36)	Study intervention administration Dose 2	7 days	7 – 9 days

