3. OBJECTIVES, ENDPOINTS, AND ESTIMANDS

Table 3 Study objectives, endpoints and estimands

Objectives	Endpoints and estimands
Primary	
To evaluate the reactogenicity and safety of the HSVTI.	
 Percentage of participants reporting each solicited administration site event (redness, pain, and swelling) within 7 days (Day 1-Day 7) post-each dose. Percentage of participants reporting each solicited systemic event (fever, fatigue, headache, myalgia, arthralgia) within 7 days (Day 1-Day 7) post-each dose. Percentage of participants reporting unsolicited AEs within 28 days (Day 1-Day 28) post-each dose. Percentage of participants reporting MAEs from Dose 1 (Day 1) up to 28 days post-Dose 2 (Day 57). Percentage of participants reporting SAEs from Dose 1 (Day 1) up to 28 days post-Dose 2 (Day 57). Percentage of participants reporting newly diagnosed pIMDs from Dose 1 (Day 1) up to 28 days post-Dose 2 (Day 57). Percentage of participants reporting exacerbation of pre-existing pIMDs from Dose 1 (Day 1) up to 28 days post-Dose 2 (Day 57). Percentage of participants reporting any hematological and biochemical laboratory abnormalities at pre-study intervention administration (Day 1), post-Dose 1 (Day 8 and Day 29), and post-Dose 2 (Day 36 and Day 57).
Secondary	
To evaluate the humoral immune response induced by the HSVTI.	
 CCI antibody GMC and seropositivity rate (assessed by ELISA) at pre-study intervention administration (Day 1), 28 days post-Dose 1 (Day 29), and 28 days post-Dose 2 (Day 57).
To evaluate the cellular immune response induced by the HSVTI.	
 Geometric mean of CCI CD4+/CD8+ T-cells frequency expressing at least 2 activation markers (IFN-γ, TNF-α, IL-2, IL-13, IL-17, 4-1BB and/or CD40L) and including at least one cytokine (assessed by CFC) at pre-study intervention administration (Day 1), 28 days post-Dose 1 (Day 29) and 28 days post-Dose 2 (Day 57).
To evaluate the safety of the HSVTI up to the end of follow-up period.	
 Percentage of participants reporting MAEs from Dose 1 (Day 1) up to study end (Day 209). Percentage of participants reporting SAEs from Dose 1 (Day 1) up to study end (Day 209). Percentage of participants reporting newly diagnosed pIMDs from Dose 1 (Day 1) up to study end (Day 209). Percentage of participants reporting pre-existing pIMDs from Dose 1 (Day 1) up to study end (Day 209).

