4. STUDY DESIGN

4.1. Overall design

[figure not shown]
This is a Phase 1, randomized, placebo-controlled, observer-blind, single-country study with 3 parallel groups (refer to Figure 1):

- **HSVTI_F1group:** approximately 20 HSV-2 seronegative participants aged 18 to 40 years will receive 2 doses of HSVTI [REDACTED].
- **HSVTI_F2 group:** approximately 20 HSV-2 seronegative participants aged 18 to 40 years will receive 2 doses of HSVTI [REDACTED].
- **Placebo group:** approximately 10 HSV-2 seronegative participants aged 18 to 40 years will receive 2 doses of placebo as control.

The study will be overseen by an iSRC (refer to Section 8.2.3).

Day 57 will be considered as the Primary Completion Date.

Figure 1 Study design overview

D: day; **HSVTI:** HSV-targeted immunotherapy **iSRC:** internal safety review committee; **N:** number of participants; **PC:** phone call; **V:** visit; **PBMC:** peripheral blood mononuclear cell

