7.2. Participant discontinuation/withdrawal from the study

A participant is considered to have withdrawn from the study if no new study procedure has been performed or no new information has been collected for them since the date of withdrawal/last contact.

From an analysis perspective, a study 'withdrawal' refers to any participant who was not available for the concluding contact planned in the protocol.

Investigators will attempt to contact participants who do not return for scheduled visits or follow-up.

All data and samples collected up to and including the date of withdrawal/last contact with the participant will be included in the study analyses.

The primary reason for study withdrawal will be documented in the eCRF, based on the list below:

- AEs requiring expedited reporting to GSK (refer to Section [10.3.11.1](#) for details)
- Unsolicited non-serious AEs
- Solicited AE
- Withdrawal by participant, not due to an AE*
- Migrated/Moved from the study area
- Lost to follow-up
- Sponsor study termination
- Other (specify)

*If a participant is withdrawn from the study because the participant has withdrawn consent and the reason for withdrawal was provided, the investigator must document this reason in the eCRF.

Participants who are withdrawn from the study because of AEs/SAEs must be clearly distinguished from participants who are withdrawn for other reasons. Investigator will follow participants who are withdrawn from the study due to an AE/SAE until the event is resolved (see Section [10.3.9.2](#)).

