
9.3.4. Secondary Endpoints/Estimands Analyses

The analysis of the secondary humoral immunogenicity objectives will be performed on the PPS for analysis of immunogenicity (PPS_immuno). The analysis of the secondary CMI objectives will be performed on the PPS for analysis of CMI (PPS_CMI). If more than 10% of participants are eliminated from any of the PPS in any treatment group, a sensitivity analysis will be carried out using the ES. The analysis of the secondary safety objective will be performed on the ES.

Statistical Analysis Methods
The percentage of participants with any AEs (solicited and unsolicited) resulting in a medically attended visit from Dose 1 up to study end (Day 209) will also be tabulated by MedDRA SOC and PT by group, after each dose and overall with exact 95% CI.
The percentage of participants with at least one report of SAE, with at least one report of causally related SAE, with at least one report of fatal SAE, and with at least one report of causally related fatal SAE classified by the MedDRA SOC and PTs reported from Dose 1 up to study end (Day 209) will be tabulated by group with exact 95% CI.
The percentage of participants with at least one newly diagnosed pIMD and at least one exacerbation of a pre-existing pIMD classified by the MedDRA SOC and PTs and reported from Dose 1 up to study end (Day 209) will be tabulated by group with exact 95% CI.
For each group, at each timepoint that blood samples are collected for immune responses and for each assay (unless otherwise specified):

• Seropositivity rates and their 95% CI will be tabulated.• GMCs/GMTs and their 95% CI will be tabulated and represented graphically. CCI [REDACTED]• Mean geometric fold increases and their 95% CI will be tabulated and represented graphically. CCI [REDACTED]• Percentage of participants that had a study intervention response defined as a 4-fold increase in concentration and their CI will be tabulated by group. CCI [REDACTED].• Antibody titer/concentration will be displayed using reverse cumulative curves.• The kinetics of titers will be plotted as a function of time for participants.• The frequency of specific CD4+/CD8+ T-cells will be summarised (mean, SD, minimum, Q1, median, Q3, and maximum) by group, at each timepoint during which blood samples are collected for CMI (descriptive statistics).

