## 3. ANALYSIS SETS

[figure not shown]
Analysis set	Description
Screened set	All participants who were screened for eligibility
Enrolled set	All participants who entered the study (who were randomized or received study intervention or underwent a post-screening procedure)
Exposed set (ES)	All participants who received at least 1 dose of the study intervention.
Per Protocol set for analysis of humoral immunogenicity (PPS_Immuno)	All eligible participants who received all doses as per protocol, have immunogenicity results post-dose, complied with dosing/blood draw intervals, without intercurrent conditions that may interfere with immunogenicity and without prohibited concomitant medication/vaccination. The analysis will be done according to the study intervention that participants received at dose 1.
Per Protocol set for analysis of cellular immunogenicity (PPS_CMI)	All eligible participants who received all doses as per protocol, have CMI results post-dose, complied with dosing/blood draw intervals, without intercurrent conditions that may interfere with immunogenicity and without prohibited concomitant medication/vaccination. The analysis will be done according to the study intervention that participants received at dose 1.

CCI

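### As legibly defined, the two per-protocol immunogenicity sets are not timepoint-specific, so a valid Day 29 result can be left out because Dose 2 was missed or off-protocol

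*Protocol*

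**What the plan says.** Protocol Section 9.2 (Table 14) defines one humoral and one cellular per-protocol set. PPS_Immuno is "All eligible participants who will receive all doses as per protocol, will have immunogenicity results post-dose, will comply with dosing/blood draw intervals", with no interfering condition and no prohibited medication or vaccination. PPS_CMI reads "All eligible participants who will receive all doses as per protocol, will have CMI results post-dose, will comply with dosing/blood draw intervals", with the same further conditions. SAP Section 3 puts the same rules in the past tense: "All eligible participants who received all doses as per protocol, have immunogenicity results post-dose, complied with dosing/blood draw intervals". None of these definitions names a timepoint.

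Section 9.3.4 assigns the secondary humoral and cellular analyses to these sets. Table 3 places those endpoints at Day 1, Day 29 (28 days after Dose 1) and Day 57 (28 days after Dose 2). The Schedule of Activities marks the Visit 3 antibody and PBMC samples with the note "Blood sampling and pregnancy test to be performed before each study intervention administration", so the Day 29 sample precedes Dose 2.

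Section 9.3.4 plans a sensitivity analysis on the ES "If more than 10% of participants are eliminated from any of the PPS in any treatment group". Section 7.1.1 lists the conditions that bar a further dose and encourages those participants to continue other procedures. The note to Table 2 says an out-of-window visit can lead to elimination, and it marks only the Visit 1 to Visit 3 and Visit 3 to Visit 5 intervals.

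**The concern.** Membership of the Day 29 analysis depends on receiving Dose 2. That dose comes after the Day 29 sample and cannot affect it, so excluding the result does nothing to protect the post-Dose 1 estimate.

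The exclusion may also be informative. Section 7.1.1 bars Dose 2 after, among other things, a related SAE, a hypersensitivity reaction, or a related AE that makes repeat exposure unsafe in the investigator's judgment. Such participants can still give a Day 29 sample. If the reaction to Dose 1 is associated with the immune response to it, the Day 29 GMC, seropositivity rate and T-cell frequency describe a selected group. Precision is lost as well.

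A second route is a dosing hold. Section 8.2.3.2 lets immunogenicity procedures continue during a hold, and Section 5.5 allows the interval between doses to extend to 90 days, against 28 to 33 days in Table 2. An in-window Day 29 sample could then belong to someone whose Dose 2 is out of window. The legible text does not say how that sample is treated.

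**Working it through.** The documents give no elimination rate and no figure behind the set definition, so there is nothing to reproduce. The check has three parts.

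**1. Order of events**
- Dose 1 is on Day 1. The Day 29 sample is drawn at Visit 3, then Dose 2 is given, and the Day 57 sample follows at Visit 5.
- The set requires all doses. With two doses planned ("approximately 20 HSV-2 seronegative participants aged 18 to 40 years will receive 2 doses of HSVTI", and likewise for placebo), a participant without Dose 2 is outside the set at every timepoint, Day 29 included.
- After Day 29 the only remaining draw for the secondary immunogenicity endpoints is Day 57. Because Table 2 says a late visit can lead to elimination, losing Day 29 for a late Day 57 draw is possible but not automatic.

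**2. When the ES analysis runs**
- Group sizes are about 20, 20 and 10 (Section 6.3.3). The condition is k/n above 10%.
- For n = 20: 2/20 = 10.0% does not trigger; 3/20 = 15.0% does.
- For n = 10: 1/10 = 10.0% does not trigger; 2/10 = 20.0% does.
- Assume an independent elimination risk d per participant, for any reason, the same in all groups and with the same status in both sets. The chance that no group triggers is P(X20 ≤ 2)² × P(X10 ≤ 1). Subtracting (1 − d)^50 gives the chance of at least one elimination with no ES analysis.

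| Assumed d | No group triggers | At least one elimination, no ES analysis |
|---|---|---|
| 2% | 97.0% | 60.6% |
| 5% | 78.1% | 70.4% |
| 10% | 33.7% | 33.2% |
| 15% | 8.9% | 8.9% |

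These are eliminations of every kind. Those that remove a valid Day 29 result because of Dose 2 or Day 57 are only part of them.

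**3. Possible size at Day 29**

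Assume 2 of 20 in one HSVTI group are left out and their values are r times those of the other 18.
- GMC(all 20) / GMC(18) = r^(2/20).
- r = 1.5: 1.041, so the per-protocol GMC is 1 − 1/1.041 = 4.0% low.
- r = 2: 1.072, so 6.7% low.
- r = 3: 1.116, so 10.4% low.
- Log-scale interval width, for equal SD: [t(17)/√18] / [t(19)/√20] = (2.110/4.243) / (2.093/4.472) = 1.063, about 6% wider.

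The direction is not known. For seropositivity, take the opposite extreme, in which the two omitted participants are seronegative and the other 18 positive. The per-protocol set then shows 18/18 = 100% (Clopper-Pearson 95% CI 81.5 to 100), against 18/20 = 90% (68.3 to 98.8) with them restored.

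**The case against.** The strongest objection is redaction. Protocol Section 9.2.1, which the Schedule of Activities and Section 6.8 cite for elimination from analysis, is blacked out, as are the SAP pages after the set table. A visit-wise rule may be there. SAP 6.1.2 bases demography on the per-protocol sets at Day 1, which may hint at sets that vary by visit. This stands: one cannot say that the plan lacks such a rule, only that the legible definition does not show one.

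Three stronger readings are tempting, and the documents do not support them.
- A reader might infer that every later visit must be in order. The Table 2 note marks two intervals only and says can; Visit 4 and the Day 209 call carry no such mark.
- A reader might infer that safety-related exclusions arise from events after Day 29. The contraindications are checked before Dose 2, so the event normally comes first and only the missed dose follows the sample.
- A reader might infer that Section 7.2 contradicts the set: "All data and samples collected up to and including the date of withdrawal/last contact with the participant will be included in the study analyses". That sentence covers participants who leave the study and names no analysis set. Section 7.1 treats stopping the intervention separately. Keeping data in the ES while omitting them from a per-protocol subset is consistent with it.

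Other safeguards count too. All safety analyses use the ES. A related SAE, or a withdrawal after a Grade 3 AE, meets a holding rule and prompts safety review, although that review does not put the Day 29 result back in the table. One fixed set also keeps the same people across timepoints, which suits the planned fold-increase and kinetics displays.

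Finally, the shift is small beside sampling error. With an assumed log10 SD of 0.3 to 0.5 (not in the documents), the 95% interval for a GMC at n = 20 spans a factor of about 1.4 to 1.7 each way.

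**Conclusion.** The point holds for the legible definition. Day 29 summaries are conditioned on Dose 2 being given per protocol, and possibly on the Day 57 draw, and the ES back-up does not cover losses of exactly 2 of 20 or 1 of 10. At those numbers no legible planned immunogenicity table would contain the omitted Day 29 results.

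The 4.0% to 10.4% GMC shift and the 6% wider interval rest on assumed losses and assumed fold differences; the documents supply neither, nor the direction. The study is descriptive, with no hypotheses and with primary endpoints on the ES. Severity is low to moderate. If the redacted elimination criteria already work by visit, what remains is a definition that should say so.

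**What to change.** In protocol Table 14 and SAP Section 3, state for both sets that:
- Day 29 analyses use compliance up to and including the Day 29 sample: Dose 1 per protocol, sample in window, and no interfering condition or prohibited product by then.
- Day 57 analyses use both doses and the Day 57 sample.

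If the elimination criteria already apply by visit, align the definition with them instead. In either case, present the Day 29 humoral and cellular tables on the ES whether or not the 10% trigger is reached.

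The cost is a few lines in two documents and a few extra tables; no new data are needed. If only the SAP is changed, its Section 4.8, now marked not applicable, needs an entry. The drawback is that denominators will differ between Day 29 and Day 57, so each table should print its own n, and displays that follow participants over time should say which set they use.
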